### 6.5 Efficacy Evaluation

#### 6.5.1 Efficacy of ARGX-117 compared to placebo on muscle strength and/or motor function in adult participants previously stabilized with IVIg

##### 6.5.1.1 Retreatment with IVIg

Summary data will be presented by treatment group. This analysis will be performed in the SAF set only.

- Time to the first retreatment with IVIg since the final IVIg treatment of the IVMP

Time to first retreatment with IVIg is defined as the time from last IVIg administration before randomization (including unscheduled visits) up to the first IVIg retreatment during DBTP.

*Time to first retreatment with IVIg = (start date of first IVIg retreatment during DBTP – stop date of last IVIg treatment before randomization)*

For participants who are not retreated with IVIg during the DBTP this will be calculated as:

*Time to first retreatment with IVIg = censoring date – stop date of last IVIg treatment before randomization*

If the stop date of last IVIg treatment before randomization is missing then the start date will be used.

The censoring date will be determined as follows:

- If the participant completes DBTP, the censoring date will be the date of last visit V14 (D113)
- If the participant early discontinues treatment, the censoring date will be the date of early discontinuation of treatment
- If the participant is ongoing in cohort 2, the censoring date will be the date of the data cutoff date

Participants who are lost to follow-up in the DBTP will be censored at the date of last visit available.

Time-to-event variables will be descriptively presented with median times, quantiles, and number and percentage of participants censored and with event (KM estimates). The probability of participants being retreated will be displayed by treatment group in the form of cumulative probability curves estimated using the non parametric Kaplan-Meier method. The CI for the median will be calculated using the Brookmeyer and Crowley method.

[REDACTED]

[REDACTED]

[REDACTED]

[REDACTED]

[REDACTED]

[REDACTED]

[REDACTED]

[REDACTED]

[REDACTED]

[REDACTED]

[REDACTED]

[REDACTED]

[REDACTED]

[REDACTED]

[REDACTED]

[REDACTED]

[REDACTED]

[REDACTED]

Time to IVIg retreatment will be listed.

- Time to relapse

Time to relapse is defined as the time from randomization up to the time participant meets threshold for clinical deterioration.

For a participant, the threshold for relapse status is met if one of these criteria is established:

[REDACTED]

*Time to relapse = (date of first clinical deterioration during DBTP – date of randomization) + 1*

The data of participants who do not meet criteria for clinical deterioration will be censored. The censoring date will be determined as follows:

- If the participant completes DBTP, the censoring date will be the date of last visit V14 (D113)
- If the participant early discontinues treatment during DBTP, without clinical deterioration, the censoring date will be the date of early discontinuation of treatment
- If the participant is ongoing in cohort 2, the censoring date will be the date of the data cutoff date

Participants who are lost to follow-up in the DBTP will be censored at the date of last visit available.

The statistical analysis will be similar to the survival analysis described above for time to first retreatment with IVIg.

Time to relapse data will be listed.

- Number of participants retreated with IVIg

The number and percentage of participants retreated with IVIg during the DBTP will be summarized by treatment. Categories will be presented as follows:

- Not retreated
- Retreated once
- Retreated twice
- Retreated more than twice
- Total number of IVIg administrations

In addition, a cross tabulation will display the status of IVIg retreatment (Yes/ No) according to the following worsening status:

- clinical deterioration [REDACTED]
- [REDACTED]
- [REDACTED]
- [REDACTED]
- [REDACTED]
- [REDACTED]

An additional table with each worsening status combined with the IVIg retreated status (IVIg retreated / Not retreated with IVIg) will be summarized as well.

- IVIg administrations during DBTP

The following endpoints will be described for participants retreated with IVIg: Number of IVIg administrations during DBTP, Total IVIg dose (g/kg), Average IVIg dose / week (g/kg) and Average IVIg dose interval (weeks)

During the DBTP, IVIg administrations reported on several visits and linked to the same visit number should be counted as a single administration. In case of IVIg administrations performed on several days for unscheduled visits, and within maximum 5 days apart from the first one to the latest one, then it should be counted as a single administration. The total number of IVIg retreatments is the sum of single IVIg administrations during DBTP. The total IVIg dose over the treatment period is the sum of doses over all single IVIg administrations.

- Number of IVIg administrations during DBTP

The number of IVIg retreatments during the DBTP will be presented.

- Total IVIg dose (g/kg)

The total IVIg dose (g/kg) during the DBTP will be presented by IVIg dose frequency subgroup.

- Average IVIg dose / week (g/kg)

The average IVIg dose per week (g/kg) during the DBTP will be presented by IVIg dose frequency subgroup.

*Average IVIg dose per week (g/kg) = Total IVIg dose / [(End DBTP date – starting date of the first IVIg retreatment+1)/7]*

- Average IVIg dose interval (weeks)

For each participant, the IVIg interval in weeks between 2 retreatments will be calculated as:

*Average IVIg dose interval (weeks) = [(Starting date of the nth IVIg retreatment – starting date of the first IVIg retreatment) / (Number of IVIg administration during DBTP-1)] / 7*

The average IVIg dose interval in weeks for participants retreated at least twice during the DBTP will be presented by IVIg dose frequency subgroup.

The number of IVIg administrations during DBTP, the total IVIg dose, the average IVIg dose pr week and the average IVIg dose interval will be listed.

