#### 3.2 Secondary Efficacy Endpoints

- **IVIg retreatment**
  - Time to the first retreatment with IVIg since the final IVIg treatment of the IVMP
  - Time to relapse
  - Number of participants retreated with IVIg
  - Number of IVIg administrations during DBTP
  - Total IVIg dose (g/kg)
  - Average IVIg dose / week (g/kg)
  - Average IVIg dose interval (weeks)
- **Endpoints derived from modified Medical Research Council (mMRC) scores:**
  - **mMRC-10 sum score**
    - Value and change from baseline in mMRC-10 sum score
    - Net incremental Area Under the Curve (iAUC) per week of the change from baseline in mMRC-10 sum score
    - Proportion of participants showing a deterioration of at least 2 points as assessed by the mMRC-10 sum score
- **mMRC-14 sum score**
  - Value and change from baseline of mMRC-14 sum score
  - Value and change from baseline in the average of the mMRC-14 sum score for the 2 most important muscle groups
- **Endpoints derived from GS:**

For each hand (the most affected and the less affected hand):

  - Value, change from baseline, percent change from baseline and maximal percent change from baseline of GS daily average
  - Net iAUC per week of the change from baseline of GS daily average
  - Value, change from baseline, percent change from baseline of GS 3-day moving average
  - Proportion of participants with > 30% reduction from baseline over 2 consecutive days of GS 3-day moving average
- **Endpoints to assess functional ability, arm and hand function, quality of life, and fatigue**
  - **MMN-RODS**
    - Values and change from baseline in MMN-RODS centile metric score
    - Values and change from baseline in MMN-RODS raw score

- 9 Hole Peg Test (9-HPT)
  - For each hand (dominant / non dominant)
    - Values, change from baseline and percent change from baseline in average time (seconds)
- EQ-5D-5L
  - For each dimension (Mobility, Self-care, Usual activities, Pain/Discomfort, Anxiety/Depression):
    - Proportion of participants by level of severity
  - For the health state VAS:
    - Value and change from baseline
- CAP-PRI
  - Values and change from baseline in CAP-PRI total score
- Patients' Global Impression of Change (PGIC)
  - Proportion of participants by level of improvement
- Fatigue Severity Scale (FSS)
  - Values and change from baseline in the FSS total score
- **Endpoints to assess health-related productivity and work productivity**
  - Health-Related Productivity Questionnaire (HRQP)

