**Double Blind Treatment Period (DBTP):**

- For the efficacy endpoints: From the first IMP administration date/time to V14 with 23:59 added as time part or date of early treatment discontinuation visit with 23:59 added as time part
- For AE and concomitant medication: From the first IMP administration date/time to:
  - Informed consent of LTE for participants who do enter into LTE. Date of informed consent corresponds to the treatment completion date in the main study. All data on the eCRF will be considered to belong to this period
  - 23h59 the day prior to the 1st FU visit at week 4 for those participants who do not enter into LTE or date of early study discontinuation with 23:59 added as time part if participant discontinued the study before FUV1
  - Date of study discontinuation with 23:59 added for participants who early discontinued study and do not enter in the safety follow up period

**DBTP and Safety Follow-up period:** For AE, from the first IMP administration date/time to:

- Informed consent of LTE for participants who do enter into LTE. Date of informed consent corresponds to the treatment completion/discontinuation date. All data on the eCRF will be considered to belong to this period
- Study discontinuation for those participants who do not enter into LTE

Participants who entered into LTE are participants who were eligible for LTE and signed the informed consent form.

**Study Day 1 IDVP:** The day of the first IVIg administration during IDVP

**Study Day 1 IVMP:** The day of the first IVIg administration during IVMP

**Study Day 1:** The day of the first administration of ARGX-117 or placebo

**Study Day 1 FU:** The day following V14/ED visit (D113) (for participants who do not enter into the LTE)

**End of Treatment Visit:** The V14 visit (D113) for participants who completed DBTP, or the visit following IMP discontinuation for participants who discontinue IMP prior to V14 (D113) or the last IMP administration date for participants who are on-going in the DBTP at the data cut-off date .

**End of Study Visit:** The V14 visit (D113) for participants entering the LTE, or the last recorded date in the DBTP or SFU period for participants not entering the LTE.

Scheduled or Unscheduled visits which do not fall into the visit windows will be listed, but not included in tables or graphs.

- **Conversion factors:**
  - 1 month = 30.4375 days
  - 1 year = 365.25 days
  - 1 week = 7 days
  - °C = (°F - 32)/1.8
- **Additional rules**

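### The average weekly IVIg dose in the DBTP is divided only by the time after first retreatment and summarised only in retreated participants, so it can mislead as a comparison between arms

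*SAP*

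**What the plan says.** SAP section 3.2 lists the average weekly IVIg dose among the secondary efficacy endpoints on IVIg retreatment. Section 6.5.1.1 then fixes four things:

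- **Label:** "The average IVIg dose per week (g/kg) during the DBTP will be presented by IVIg dose frequency subgroup".
- **Formula:** "Total IVIg dose / [(End DBTP date – starting date of the first IVIg retreatment+1)/7" (the closing bracket follows).
- **Numerator:** "The total IVIg dose over the treatment period is the sum of doses over all single IVIg administrations".
- **Who is summarised:** "The following endpoints will be described for participants retreated with IVIg". The number of administrations, the total dose and the average dose interval fall under the same restriction.

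The section opens with "Summary data will be presented by treatment group. This analysis will be performed in the SAF set only", so the results are set out by arm. Section 5.2 defines the DBTP for efficacy endpoints as running "From the first IMP administration date/time to V14 with 23:59 added as time part or date of early treatment discontinuation visit". The visible text has no full-period version of the weekly dose and no version covering all participants.

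**The concern.** The label and the denominator cover different periods. The label says DBTP, which by section 5.2 starts at the first dose of investigational product (IMP). The denominator starts at the first retreatment. The weeks a participant manages without IVIg, which an effective drug should lengthen, never enter the rate.

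Three consequences follow:

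- For a given total dose, a later first retreatment gives a higher weekly dose. A first retreatment close to the end of the DBTP gives an extreme value.
- A participant who is never retreated drops out of the summary instead of contributing 0.
- Retreatment is an outcome. Comparing arms only among the retreated therefore compares subsets selected after randomisation.

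A reader who takes the weekly dose at face value as a measure of IVIg use could conclude that the arm needing less IVIg needs more.

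**Working it through.** The SAP gives no value for this endpoint, so there is no planned figure to reproduce. The check applies the stated formula and compares it with a full-period rate.

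**Inputs from the SAP:** the formula, the restriction to retreated participants, and DBTP end at V14 = day 113.

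**Assumptions not in the SAP:** 1 g/kg per administration, the repeat interval, and an exponential time to first retreatment.

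**Formulas**, with *t* the day of first retreatment and *D* the total dose:

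- SAP: *D* / [(113 − *t* + 1)/7]
- Full period: *D* / (113/7), that is *D* / 16.14

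**Two participants**

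| Pattern | Total (g/kg) | SAP formula (g/kg/week) | Full DBTP (g/kg/week) |
|---|---|---|---|
| Days 22, 50, 78, 106 | 4 | 4 × 7/92 = 0.304 | 4 × 7/113 = 0.248 |
| Day 106 only | 1 | 1 × 7/8 = 0.875 | 1 × 7/113 = 0.062 |

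The second participant used a quarter of the IVIg and scores 0.875/0.304 = 2.9 times higher.

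**One 1 g/kg dose, by day given.** Day 22: 0.076. Day 57: 0.123. Day 85: 0.241. Day 106: 0.875. Day 113: 7.0. The full-period rate is 0.062 each time. Early discontinuation has the same effect because it moves the end date: stopping the day after a single dose gives 1 × 7/2 = 3.5.

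**Group level.** Median time to first retreatment 40 days in one arm and 270 in the other, repeats every 28 days, 1 g/kg, end day 113. The shares retreated are 1 − 2^(−113/40) = 86% and 1 − 2^(−113/270) = 25%.

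| g/kg/week | Median 40 days | Median 270 days |
|---|---|---|
| SAP formula, mean among retreated | 0.355 | 0.452 |
| SAP formula, median among retreated | 0.292 | 0.304 |
| SAP formula, mean without first retreatments from day 107 on | 0.308 | 0.332 |
| Full DBTP, all participants, mean | 0.165 | 0.041 |

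The gap in means is 0.452 − 0.355 = 0.097. Without first retreatments in the last 7 days it is 0.332 − 0.308 = 0.024, so about three quarters of it comes from that week.

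**Sensitivity to the assumptions.** With medians of 28 and 280 days, the means among the retreated are:

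| Repeat pattern | Median 28 days | Median 280 days |
|---|---|---|
| Every 2 weeks | 0.573 | 0.685 |
| Every 4 weeks | 0.327 | 0.453 |
| Every 5 weeks | 0.282 | 0.410 |
| Single dose | 0.138 | 0.307 |

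The means reverse in every case.

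**At the planned size.** A 2:1 split of 24 gives 16 active and 8 placebo per cohort. With medians of 28 (placebo) and 140 days (active) and 4-weekly repeats, the active mean exceeds the placebo mean in about 76% of simulated trials under the SAP formula. Under the full-period, all-participant definition it does so in about 0.1%.

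**The case against.** **The formula describes something legitimate.** It gives dose intensity once IVIg has been restarted. The average-interval formula beside it is also anchored at the first retreatment, which suggests a deliberate post-retreatment description, and the restriction to retreated participants is stated openly. This stands as a reason to keep the statistic under its own name. It does not justify presenting it as the DBTP average.

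**The reversal is mostly in the mean.** Section 6.2.1 requires the median, quartiles, minimum and maximum as well, so a reader would see the outliers, and the medians barely differ. This stands, and it limits the size of the problem.

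**Other summaries point the right way.** Time to first retreatment is analysed by Kaplan-Meier in the whole Safety Set. The table of retreatment categories in section 6.5.1.1 includes those not retreated. Total dose has no faulty denominator and, even among the retreated, averages 3.11 versus 2.62 g/kg in the 40-versus-270-day simulation, which is the right order. The components are also listed per participant, so the full-period rate could be recomputed. All of this stands.

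**Two stronger readings are tempting and not supported.** One is that avoiding IVIg raises the reported weekly dose. It does not: a participant who avoids IVIg leaves the summary. Delay raises the value without exception only for a fixed total dose. With repeat dosing the value moves in a sawtooth (3-weekly repeats: 0.412 from day 29, 0.368 from day 57, 0.483 from day 85). The other is that the trial would reach a wrong conclusion about efficacy. The primary objective is safety, no formal hypothesis test is planned, and no visible text ties a decision to this endpoint.

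**Conclusion.** The point holds as a defect of definition and label in a secondary descriptive endpoint. The statistic omits IVIg-free time and never-retreated participants, and a first retreatment near the end of the DBTP can dominate a group mean. The SAP also splits the summary by IVIg dose frequency subgroup, where cells are smaller still.

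The mismatch of label, denominator and population follows from the text alone. The sizes rest on the assumed dose, repeat intervals and retreatment times. The direction of the means did not depend on which repeat pattern was tried, while the medians hardly moved. Because the time-to-retreatment analysis and the retreatment-category table would show the true direction, this should be fixed but does not threaten the trial's overall conclusion.

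**What to change.** In SAP section 6.5.1.1, define the average IVIg dose per week during the DBTP as total IVIg dose / [(end of DBTP date − date of first IMP + 1)/7], for every Safety Set participant, with 0 for those not retreated. Summarise total IVIg dose in all Safety Set participants in the same way.

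If the current formula is kept, name it IVIg dose intensity after first retreatment and present it only as a supplementary statistic.

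The cost is SAP wording, one derivation, and a rerun of Table 14.2.1.5 and the related IVIg exposure listing. No new data are needed.

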#### 6.5.1.2 Modified Medical Research Council (mMRC)

The mMRC sum scores evaluate motor strength/weakness from predetermined muscle groups (upper and lower limbs). Each muscle group is scored from 0 (paralysis) to 5 (normal strength). The total score is based on the sum of both the left and right side of the body. The mMRC-10 Sum Score assesses 10 groups of muscles yielding to a total score from 0 to 100 and the mMRC-14 Sum Score assess 14 groups of muscles yielding to a total score from 0 to 140 (Table 15).

**Table 15 Muscle Groups Tested for Each mMRC Sum Score**

Muscle Groups Tested on Both Sides	mMRC 10-Sum Score	mMRC 14-Sum Score
Upper limbs		
Shoulder abductors	X	X
Elbow flexors	X	X
Elbow extensors	X	X
Wrist extensors	X	X
Wrist flexors	X	X
Finger flexors		X
Finger extensors at metacarpophalangeal joints		X

- Net iAUC per week of the change from baseline in mMRC-10 sum score

Net iAUC of the change from baseline in mMRC-10 sum score is defined as the total area under the curve which is above 0 (ie, positive) minus the area below 0. It will be derived using a linear trapezoidal rule.

#### **Net iAUClast assessment per Week**

*Net iAUClast assessment per week = [(iAUCv1-v3 + iAUCv3-v4 + ... + iAUCvn-1-vn) / ((date of last analysis visit during DBTP – date of baseline + 1) / 7)], where n is the last analysis visit number of mMRC-10 assessment with available data.*

The calculation of net iAUClast assessment per week is detailed in appendix 9.4.

If net iAUC is positive [resp. negative] it would imply that there is an improvement [resp. deterioration] on mMRC-10 sum score. If a score is missing at a post baseline visit, the iAUC will be calculated from the last non missing available assessment up to the next non missing assessment.

Net iAUC per week will be displayed by treatment group and overall using descriptive statistics.

#### **Partial Net iAUC**

Net iAUCday1- week4, net iAUCday1- week8, net iAUCday1- week12, and net iAUCday1- week16 will be derived.

If the final landmark time point is missing (week 4, week 8, week 12 and week 16 for net iAUCday1- week4, net iAUCday1- week8, net iAUCday1- week12, and net iAUCday1- week16), the net iAUC will be considered missing. If an intermediate time point is missing the intermediate data point will be considered as missing, the partial net iAUC will be calculated from the last non missing available assessment up to the next non missing assessment within the interval.

Net iAUCday1- week4, net iAUCday1- week8, net iAUCday1- week12, and net iAUCday1- week16 will also be presented for participants who have an assessment of mMRC-10 sum score at week 4, week 8, week 12 or week 16, respectively.

- Proportion of participants showing a deterioration of at least 2 points as assessed by the mMRC-10 sum score

The number and percentage of participants showing a deterioration of at least 2 points in mMRC-10 sum score at last assessment during IVMP compared to IVMP baseline will be summarized.

On the DBTP, the number and percentage of participants showing a deterioration of at least 2 points in mMRC-10 sum score compared to baseline at last assessments derived visits (as defined in 6.2.1.2) will be summarized.

mMRC-10 Sum Score data will be listed.

**mMRC-14 sum score**

mMRC-14 sum score will be re-derived and used for the analysis.

- Value and change from baseline in mMRC-14 sum score

On the IVMP, actual value and change from IVMP baseline of mMRC-14 sum score will be computed for each visit.

On the DBTP, actual value and change from baseline of mMRC-14 sum score will be computed for each visit (as defined in 6.2.1.2).

[REDACTED]

- Value and change from baseline of the average of the mMRC-14 scores for the 2 most important muscle groups

For each visit, the mMRC-14 score for the 2 most important muscle groups will be averaged. If at least one value of one of the 2 most important muscle groups is missing, the average will be considered as missing.

On the IVMP, actual value and change from IVMP baseline of the average of the mMRC-14 score for the 2 most important muscle will be computed for each visit.

On the DBTP, the actual value and change from baseline of the average of the mMRC-14 score for the 2 most important muscle will be computed for each visit (as defined in 6.2.1.2).

mMRC-14 Sum Score data will be listed.

**6.5.1.3 Grip strength (GS)**

Hand GS measurements consist of 3 repeated contractions with the right hand followed by 3 repeated contractions with the left hand. GS are assessed on-site at trial visits and monitored daily.

These analyses will be performed in the SAF set.

The variables computed by eCOA and used for the analyses are in detailed in section 6.2.1.1 and appendix 9.3. Analysis will be performed as defined in 6.2.1.2.

**GS Daily Average**

The GS daily average will be derived for the most and less affected hand separately. If at least one value is missing for the most or less affected hand, the GS daily average will be considered as missing for the corresponding hand.

- Value, Change from baseline and percent change from baseline and maximal percent change of GS daily average

On the IVMP, actual value and change from IVMP baseline and percent change from baseline GS daily average will be summarized at last assessment for each hand (most affected and less affected).

On the DBTP, for each hand (most affected and less affected), the actual value and change from baseline and percent change from baseline GS daily average will be summarized at last assessments (as defined in 6.2.1.2).

For the computation of the percent change from baseline (either at IVMP baseline or DBTP baseline), in case of value of baseline equal to 0 for GS daily average, the value of baseline for the denominator will be imputed by 1.

[REDACTED]

- Net iAUC per week of the change from baseline of GS daily average

For each hand (most affected and less affected), net incremental AUC (net iAUC) of the change from baseline up to last assessment during DBTP will be derived using linear trapezoidal rule and standardized per week as follows:

